5.4 FOLLOW-UP ASSESSMENTS

5.4.1 Follow Up for Safety

Patients must have a safety evaluation 30-45 days after the last dose of study drug (ie, 30 days +15-day window). This evaluation can be done by phone. The following assessments will be performed:

- Assess for AEs
 - Ongoing AEs must be followed clinically until they resolve, are deemed permanent or no longer clinically significant, or the patient begins an alternative treatment regimen
- Record only those medications (prescription, nonprescription, and nutritional supplements) administered in conjunction with an AE, as well as any antineoplastic therapies initiated since discontinuation of study drug.

5.4.2 Follow Up for Overall Survival

All patients enrolled and treated in the Phase 2 study will be contacted by telephone to assess for date of death, date of stem cell transplant, date of relapse, or continued remission for three years:

- Year 1: Phone calls monthly beginning the month after the patient completes the end-of-study assessments to 12 months after Date of First Dose regardless of how many cycles a patient receives (Year 1 = Date of First Dose plus 12 months)
- Year 2: Phone calls every other month during Year 2 (months 14 to 24 months after Date of First Dose).
- Year 3: Phone calls every three months during Year 3 (months 25 to 36 months after Date of First Dose).

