Efficacy Endpoints:	
Phase 2
 
Primary Efficacy Endpoints
 
Assess preliminary efficacy, as determined by response rate, duration of response, hematological improvement, rate of transfusion independence, time to acute myeloid leukemia (AML), and overall survival (OS). 
Efficacy endpoints will be any objective response to study drug therapy using assessments defined by the 2006 revised International Working Group (IWG) and European MDS Working Group.
 
Secondary Efficacy Endpoints
 
The proportion of MDS patients in the overall population achieving RBC transfusion independence with duration ≥ 84 days (12 weeks) during treatment. Baseline RBC transfusion dependency is defined as an average transfusion requirement of ≥ 2 units/28 days of RBCs without any consecutive 28-day gaps between transfusions for a minimum of 56 days immediately preceding first dose. Transfusion data include the hemoglobin value for which the transfusion was administered and must have been ≤ 10.0 g/dL within 7 days prior to transfusion administration to be counted toward the RBC transfusion-dependent status.Platelet transfusion independence with duration ≥ 84 days (12 weeks) will be assessed in the proportion of patients who were platelet transfusion-dependent at baseline. Baseline platelet transfusion requirements are established by the number of platelet transfusions administered during the 56 days immediately preceding and including the date of first dose.Erythroid hematologic improvement and platelet hematologic improvement will be assessed according to the 2006 revised IWG criteria.Correlation of complete response rates with BH3 profiling results including MCL-1 dependencyOverall survival compared to historical survival 
Complete details of the planned analysis will be documented in a full Statistical Analysis Plan (SAP), which will be finalized before locking the study database.

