7.2 EFFICACY ENDPOINTS

Primary Efficacy Endpoints

- Assess preliminary efficacy, as determined by response rate, duration of response, hematological improvement, rate of transfusion dependence, time to AML, and overall survival.

Efficacy endpoints will be any objective response to study drug therapy using assessments defined by the 2006 revised International Working Group (IWG) criteria [28] and European MDS Working Group.

Secondary Efficacy Endpoints

- The proportion of MDS patients in the overall population achieving RBC transfusion independence with duration ≥ 84 days (12 weeks) during treatment. Baseline RBC transfusion dependence is defined as an average transfusion requirement of ≥ 2 units/28 days of RBCs without any consecutive 28-day gaps between transfusions for a minimum of 56 days immediately preceding first dose. Transfusion data include the hemoglobin value for which the transfusion was administered and must have been ≤ 10.0 g/dL within 7 days prior to transfusion administration to be counted toward the RBC transfusion-dependent status.

- Platelet transfusion independence with duration ≥ 84 days (12 weeks) will be assessed in the proportion of patients who were platelet transfusion dependent at baseline. Baseline platelet transfusion requirements are established by the number of platelet transfusions administered during the 56 days immediately preceding and including the date of first dose.
- Erythroid hematologic improvement and platelet hematologic improvement will be assessed according to International Working Group 2006 criteria.
- Correlation of complete response rates with BH3 profiling results including MCL-1 dependency
- Overall survival compared to historical data

Complete details of the planned analysis will be documented in a full Statistical Analysis Plan (SAP), which will be finalized before locking the study database.

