11.9 EFFICACY ANALYSIS

The efficacy endpoints include the following:

- Complete Response Rate (CRR) is the percentage of patients achieving a CR, CRi, CRmarrow, PR, or HI. Patients who, for any reason, do not supply bone marrow for response assessment are counted among those not achieving CR/CRi/CRmarrow/PR/HI. CRR will be summarized by number and percentage of patients meeting the definition of CRR along with the corresponding exact 95% confidence intervals.
- Duration of response and time to AML will be summarized by Kaplan-Meier methods (median, 95% CI, number of events, number censored, and Kaplan-Meier figures),
- Hematological improvement and rate of transfusion independence will be summarized using the appropriate descriptive statistics and 95% confidence intervals.
- Overall survival (OS), defined as the time from first dose to death from any cause. OS will be summarized by Kaplan-Meier methods (median, 95% CI, number of events, number censored, and Kaplan-Meier figures).

Descriptive statistics will also be calculated for each secondary measure of efficacy.

- The proportion of MDS patients in the overall population achieving RBC transfusion independence with duration ≥ 84 days (12 weeks) during treatment. Baseline RBC transfusion dependency is defined as an average transfusion requirement of ≥ 2 units/28 days of RBCs without any consecutive 28-day gaps between transfusions for a minimum of 56 days immediately preceding first dose. Transfusion data include the hemoglobin value for which the transfusion was administered and must have been ≤ 10.0 g/dL within 7 days prior to transfusion administration to be counted toward the RBC transfusion-dependent status.
- Platelet transfusion independence with duration ≥ 84 days (12 weeks) will be assessed in the proportion of patients who were platelet transfusion-dependent at baseline. Baseline platelet transfusion requirements are established by the number of platelet transfusions administered during the 56 days immediately preceding and including the date of first dose.

- Erythroid hematologic improvement and platelet hematologic improvement will be assessed according to the 2006 revised IWG criteria [28].

Additional analyses may be performed to assist the sponsor in planning future studies.

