APPENDIX F – REVISED INTERNATIONAL WORKING GROUP (IWG) RESPONSE CRITERIA (2006)

Category	Response criteria (responses must last at least 4 wk)
Complete remission	Bone marrow: $\leq 5\%$ myeloblasts with normal maturation of all cell lines* Persistent dysplasia will be noted† Peripheral blood‡ Hgb ≥ 11 g/dL Platelets $\geq 100 \times 10^9/L$ Neutrophils $\geq 1.0 \times 10^9/L$ † Blasts 0%
Partial remission	All CR criteria if abnormal before treatment except: Bone marrow blasts decreased by $\geq 50\%$ over pretreatment but still $> 5\%$ Cellularity and morphology not relevant
Marrow CR†	Bone marrow: $\leq 5\%$ myeloblasts and decrease by $\geq 50\%$ over pretreatment† Peripheral blood: if HI responses, they will be noted in addition to marrow CR†
Stable disease	Failure to achieve at least PR, but no evidence of progression for > 8 wks
Failure	Death during treatment or disease progression characterized by worsening of cytopenias, increase in percentage of bone marrow blasts, or progression to a more advanced MDS FAB subtype than pretreatment
Relapse after CR or PR	At least 1 of the following: Return to pretreatment bone marrow blast percentage Decrement of $\geq 50\%$ from maximum remission/response levels in granulocytes or platelets Reduction in Hgb concentration by ≥ 1.5 g/dL or transfusion dependence
Cytogenetic response	Complete Disappearance of the chromosomal abnormality without appearance of new ones Partial At least 50% reduction of the chromosomal abnormality

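### Minor: time to AML is a Phase 2 primary endpoint, but the follow-up calls to month 36 carry no AML item and no rule covers death without AML

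*Protocol*

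**What the plan says.** Protocol Section 7.2 puts time to AML under the primary efficacy endpoints, in a list that ends "rate of transfusion dependence, time to AML, and overall survival". The synopsis and SAP Section 3.7.2 also list it as primary for Phase 2. Protocol Section 11.9 gives the method: "Duration of response and time to AML will be summarized by Kaplan-Meier methods". The same section defines survival fully, "Overall survival (OS), defined as the time from first dose to death from any cause", but gives no origin, event or censoring rule for time to AML.

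Section 5.4.2 has all treated Phase 2 patients "contacted by telephone to assess for date of death, date of stem cell transplant, date of relapse, or continued remission for three years", counted from first dose.

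Appendix F has a category "Relapse after CR or PR" and a separate one for relapse after hematologic improvement. Any one listed criterion is enough for relapse after CR or PR, and the last is a hemoglobin fall of at least 1.5 g/dL "or transfusion dependence". Appendix F lists overall, event-free, progression-free and disease-free survival and cause-specific death. It does not list time to AML.

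Sections 7.2 and 11.1 leave analysis detail to the SAP. SAP Section 11 covers best response, cytogenetic response and hematologic improvement, and plans no time-to-AML analysis.

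**The concern.** A time-to-event endpoint needs a defined event, a defined start, a way to find the event throughout follow-up, and a rule for patients who die first. Time to AML has a named method but none of the first, second or fourth, and the third lapses once treatment has ended.

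With no AML question, the analyst would have to choose between counting unassessed patients as AML-free, which understates incidence, and censoring them at their last assessment, which discards most of the follow-up. With no rule for death, a Kaplan-Meier analysis that censors deaths would overstate AML incidence. A SAP could settle the estimator afterwards, but it could not supply AML dates that nobody had been asked to record.

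**Working it through.** **1. The plan's own figures.** The documents give no event count, rate or power for time to AML, so there is nothing to reproduce for this endpoint. The Phase 2 operating characteristics concern response only. The rule is to stop at 1 or fewer of 15 and to call the regimen worthwhile at 6 or more of 25. Summing P(X₁ = x)·P(X₂ ≥ 6 − x) over x = 2 to 15, with X₁ ~ Bin(15, p) and X₂ ~ Bin(10, p), gives 0.033 at p = 10% (stated Type I error 0.05) and 0.802 at p = 30% (stated power 80%). That design holds and does not involve AML.

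**2. Where AML could be seen.**

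| Period | Protocol text | AML date? |
|---|---|---|
| On treatment | 5.2.2.6: marrow at Cycles 2, 4, 6, then every 4 cycles; also when clinically needed or at progression | Can be derived |
| End of Study | 5.3: examination and hematology panel for all; marrow only if 8 weeks or more since the last response assessment | Often |
| 30–45 days after last dose | 5.4.1: adverse events, new antineoplastic therapy | Incidental |
| Then to month 36 | 5.4.2: death, transplant, relapse, remission | No item |
| At death | 8.7: cause of death | Incidental; the date is that of death |

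**3. Whether relapse covers it.** A nonresponder has nothing to relapse from, so AML in that patient fits no call item. Section 6.2 has patients without a response considered for removal after Cycle 2, so this group can leave early. In a responder, relapse can be declared on hemoglobin or transfusions alone, so its date is not an AML date.

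**4. Whether the event is fixed elsewhere.** It is not. The Appendix F progression table has brackets that cross at 20% and at 30% blasts, including one for patients starting at 20–30%. The choice of blast threshold therefore changes who can have an event, and none is stated.

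**5. Share of follow-up without an AML question.** Inputs: 28-day cycles (Section 5.2.2.6 places Day 1 of the next cycle straight after Day 28), 36 months from first dose (5.4.2), and 30.4375 days per month (SAP 8.6). Share = (36 − months to end of last cycle)/36. The alternative start is the latest safety contact: last alvocidib dose on Day 10 of the final cycle plus 45 days.

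| Cycles | End of last cycle | Share | Latest safety contact | Share |
|---|---|---|---|---|
| 2 | day 56 = 1.84 mo | 95% | day 83 = 2.73 mo | 92% |
| 4 | day 112 = 3.68 mo | 90% | day 139 = 4.57 mo | 87% |
| 6 | day 168 = 5.52 mo | 85% | day 195 = 6.41 mo | 82% |
| 12 | day 336 = 11.04 mo | 69% | day 363 = 11.93 mo | 67% |

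These are shares of the planned window for a patient who lives through it.

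**6. Effect of the missing rule for death.** This is an illustration with complete AML capture. Assume constant hazards, true 36-month AML incidence A = 30%, and death without AML D = 10%, 30% or 50%. With F = A + D, censoring deaths gives 1 − KM = 1 − exp[(A/F)·ln(1 − F)].

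- D = 10%: 1 − exp(0.75 × ln 0.60) = 31.8%
- D = 30%: 1 − exp(0.50 × ln 0.40) = 36.8%
- D = 50%: 1 − exp(0.375 × ln 0.20) = 45.3%

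Cumulative incidence with death as a competing event returns 30% in each case. AML-or-death gives F itself: 40%, 60% or 80%. The same patients therefore yield quite different figures depending on a rule that the plan does not state.

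**The case against.** The best case on the other side has four parts.

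- **Weight.** Section 11.1 calls the analysis mainly descriptive, with no formal testing. Time to AML is one of six items in a single primary bullet, and the Phase 2 decision rests on response. The SAP records zero Phase 2 patients and a closed study. This stands, and it is why the point is minor.
- **Deferral.** Sections 7.2 and 11.1 leave method to the SAP, and SAP Section 7.2 foresaw a separate Phase 2 analysis. A Phase 2 SAP could have fixed the origin, event and estimator. This stands for those, but not for what the calls ask.
- **Capture.** Assessments at progression or when clinically needed, and the unconditional End of Study blood count and examination, would pick up AML on treatment and around its end. This stands, and it confines the gap to later follow-up.
- **Inputs.** The 30% follows the figure in Section 1.1, which is for all patients diagnosed with MDS and has no time horizon. Phase 2 admits IPSS-R intermediate risk and above, whose AML risk Section 1.2 calls increased. This stands, so the figures in step 6 show direction and scale and do not forecast this trial.

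A reader might infer that AML dates would certainly not have been collected. The documents do not show that. Section 5.4.2 lists call topics, and the annotated case report form and data dictionary cited in SAP Section 1 were not available to check. The supported statement is that no protocol text requires an AML date after the end-of-treatment contacts.

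**Conclusion.** The point holds, as a minor one, for the protocol as written and for any reuse of the design. A Phase 2 primary endpoint has no planned AML question over about 69% to 95% of the 36 months for patients stopping after 12 to 2 cycles. It also has no stated event, origin or treatment of death without AML. The coverage shares follow from the schedule. The 31.8% to 45.3% range rests on assumed constant hazards, an assumed 30% incidence and assumed death rates.

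Three stronger readings are not supported:

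- **That a result of this study is affected.** It is not: no patient entered Phase 2, and the go/no-go rule does not use AML.
- **That Kaplan-Meier is wrong in itself.** It overstates AML incidence only if deaths are censored and 1 − KM is read as incidence. For AML-free survival it is suitable.
- **That stopping AML assessment at the end of treatment must bias the estimate.** Censoring there loses information. Bias would need AML risk to change after treatment stops, and the documents give no data on that.

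Nor does the SAP need a further note on the unanalysed endpoint. It already says that efficacy will not be analysed inferentially, that Phase 2 enrolled nobody, and that the tables cover Phase 1b only.

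**What to change.** 1. In Section 5.4.2, add 'date and basis of AML diagnosis' to the items asked on the existing calls, for every Phase 2 patient whether or not they responded, with a matching data field.
2. In Section 11.9, define time to AML from first dose, as for overall survival, with a stated AML event. Estimate it by the cumulative incidence function (Aalen-Johansen), with death without AML as a competing event and censoring at the last AML assessment. Alternatively, report Kaplan-Meier AML-free survival, with AML or death as the event.

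The cost is one question on calls already scheduled and a sentence or two of definition. No visit, sample, treatment or sample-size change is needed. With Phase 2 closed unopened, the changes belong in any protocol that reuses this design.

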6. OFF-STUDY CRITERIA

6.1 WITHDRAWAL OF PATIENTS

All patients have the right to withdraw at any time during treatment without prejudice. Circumstances may occur under which a patient may be permanently removed from the study. The criteria used to justify withdrawal of a study patient are described below.

In the event of a premature withdrawal, the assessments for the End of Study visit, as detailed in the Schedule of Activities ([Appendix A](#)), should be completed at the time of the withdrawal, wherever possible, including dates of response and death. If the study patient is prematurely withdrawn due to an AE, attempts should also be made to clinically follow the study patient until the event is resolved, stable or permanent as determined by the PI and Sponsor.

6.2 REASONS FOR WITHDRAWAL

A patient may be permanently removed from the study for any of the following reasons:

- Failure to achieve a response. Patients not demonstrating evidence of CR/CRi/CRmarrow/PR/HI after the second cycle of treatment will be considered for removal from the study, although with permission of the Medical Monitor, induction treatment may continue if clinically indicated and provided there is no evidence of toxicity \geq NCI CTCAE grade 4;
- An excessive Grade 3-4 toxicity without a response to treatment or occurrence of any other AE, concurrent illness or laboratory abnormality which, in the opinion of the PI, warrants the patient's permanent withdrawal;
- Patient noncompliance, defined as refusal or inability to adhere to the study schedule;
- At the request of the patient, PI, the Sponsor, or regulatory authority;
- Patient is lost to follow-up;
- Patient becomes pregnant while on study;
- Patient begins another treatment for their disease; or
- Patient death.

6.3 FOLLOW-UP FOR PATIENTS WITHDRAWN FROM STUDY

Patients withdrawn from the study with an ongoing AE must be followed clinically until the event is resolved, deemed stable or permanent, or the patient begins an alternative treatment regimen. A stable adverse event is defined as an event that is not expected to change in nature, severity or frequency. See [Sections 8.4 – 8.8](#) for reporting of adverse events. Patients withdrawn from the study for pregnancy will be followed according to [Section 5.4](#). The pregnancy of any patient, or patient's partner, will be followed to term to record any birth defects/abnormalities at time of birth.

6.4 TERMINATION OR SUSPENSION OF STUDY

Should the Sponsor or their representatives, Investigators, or appropriate regulatory officials discover conditions during the study that indicate that the study or site involvement should be put 'On Hold' or 'Terminated', this action may be taken after appropriate consultation with the Sponsor, Investigators and Study Monitors.

Conditions that may warrant termination of the study or involvement of a study site include, but are not limited to:

- If the Data Safety Monitoring Board (DSMB)* recommends stopping the study due to safety concerns (*if applicable, as DSMBs may not be utilized in every study);
- The decision on the part of the Sponsor to suspend or discontinue testing, evaluation, or development of the study drug
- The discovery of an unexpected, serious, unacceptable risk to patients enrolled in the study;
- Failure of the Investigator(s) to comply with pertinent clinical trial regulations; or
- Submission of knowingly false information from the research facility to the Sponsor, study monitor, or regulatory agencies.
- Insufficient adherence to protocol requirements.

Study termination and follow-up will be performed in compliance with the conditions set forth in the International Council on Harmonisation (ICH) sixth efficacy publication (E6) on Good Clinical Practice (GCP), Section 4.12, ICH E6 4.13, ICH E6 5.20, and ICH E6 5.21, with appropriate notification of the Food and Drug Administration (FDA) and all IRBs having approved the study protocol and ICF.

7. CRITERIA FOR EVALUATION

7.1 SAFETY ENDPOINTS

Safety and tolerability of alvocidib when administered in sequence after DEC (**during dose escalation**) or AZA will be assessed by analyzing the DLTs, MTD, and incidence rates of treatment-emergent adverse events (TEAEs) summarized within treatment group(s) at the MedDRA preferred term and primary system organ class levels. Similar summaries will be made for subsets of AEs such as (1) those judged by the Investigator to be related to study treatment, and (2) serious adverse events (SAEs).

Other routine safety assessments (eg, physical examinations, vital sign measurements, and clinical laboratory testing [hematology, serum chemistry, and coagulation]) will be analyzed as additional measures of safety and tolerability for the entire study duration. These assessments will be summarized by shift tables and treatment group using mean, standard deviation, median, minimum and maximum changes from baseline values.

Mortality (all causes) will be calculated.

7.2 EFFICACY ENDPOINTS

Primary Efficacy Endpoints

- Assess preliminary efficacy, as determined by response rate, duration of response, hematological improvement, rate of transfusion dependence, time to AML, and overall survival.

Efficacy endpoints will be any objective response to study drug therapy using assessments defined by the 2006 revised International Working Group (IWG) criteria [28] and European MDS Working Group.

Secondary Efficacy Endpoints

- The proportion of MDS patients in the overall population achieving RBC transfusion independence with duration ≥ 84 days (12 weeks) during treatment. Baseline RBC transfusion dependence is defined as an average transfusion requirement of ≥ 2 units/28 days of RBCs without any consecutive 28-day gaps between transfusions for a minimum of 56 days immediately preceding first dose. Transfusion data include the hemoglobin value for which the transfusion was administered and must have been ≤ 10.0 g/dL within 7 days prior to transfusion administration to be counted toward the RBC transfusion-dependent status.

- Platelet transfusion independence with duration ≥ 84 days (12 weeks) will be assessed in the proportion of patients who were platelet transfusion dependent at baseline. Baseline platelet transfusion requirements are established by the number of platelet transfusions administered during the 56 days immediately preceding and including the date of first dose.
- Erythroid hematologic improvement and platelet hematologic improvement will be assessed according to International Working Group 2006 criteria.
- Correlation of complete response rates with BH3 profiling results including MCL-1 dependency
- Overall survival compared to historical data

Complete details of the planned analysis will be documented in a full Statistical Analysis Plan (SAP), which will be finalized before locking the study database.

